5.0 Study Endpoints

Primary Outcomes

Relapse will be defined as percent drinking or drug use days postpartum and by drug screen at hospital admission results.

Postpartum PTSD severity – PTSD Checklist score

Postpartum depression severity – Edinburgh Postpartum Depression Scale Score

Breastfeeding Uptake

Neonatal Abstinence Syndrome

Length of NICU Stay

Secondary Outcomes

Social Support – NIH Toolbox

Labor and Delivery Autonomy

Participant Satisfaction

Doula Satisfaction

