6.0 Procedures Involved*

We will offer doula services at no cost to the 15-17 women (G1) who screen into the study and have a comparison group of 15-17 women with no doulas (TAU).

We will recruit 30-34 pregnant women (to have a final sample size of 30 women) at the XXX Program. Women in G1 will be assigned a doula. The 2nd group (G2

PROTOCOL TITLE: Providing Expanded Continuous Labor Support to Pregnant Women in New Mexico with Substance Use Disorders

Treatment as Usual) will be asked if they would potentially be interested in doula care, but will not be assigned a doula. We will conduct baseline (covariates/ dependent variables) and postpartum (outcome variables) behavioral health assessments, as well as a chart review (outcome variables and covariates).

Assessment. All questionnaires are well-validated and will be administered electronically (e.g. Qualtrics) or on paper. Baseline assessment will immediately follow screening and consent at the XXX Clinic, unless participants request more time to review the consent form or can't stay at the Clinic that day. In this case, a follow-up appointment will be made to conduct consent and/or assessments, which may then occur at the XXX Clinic or at XXX. Follow-up outcomes will be assessed at postpartum follow-ups (PPFU), ideally in the XXX Clinic, but when necessary at XXX, via the telephone, or via an online form and also by chart review. See Chart Review section below for details. Additionally, doulas will fill out a doula satisfaction survey online following each 2-week postpartum doula visit. Participants will be asked to provide a list of “locators” – people who will be able to help us find them if we lose contact before the PPFU visit. We will use a “Locator” form developed by XXX for this. This information will be stored with PII, separate from all PHI and ID numbers.

Table 1. Purpose – Measure	Baseline	2-wk PPFU
Screener – Study specific form	X	
Traumatic Life Events – Life Events Checklist - 5 ³⁸	X	X
Prenatal PTSD – PTSD Checklist - 5 ³⁹	X	X
Perinatal Depression – Edinburgh Postpartum Depression Scale ⁴⁰	X	X
Substance Use Disorders – Structured Clinical Interview for DSM5-E ⁴¹	X	
Demographics – Study specific form	X	
Current substance use – Timeline Followback ⁴²	X	X
Social Support – NIH Toolbox ⁴³	X	X
Labor & Delivery Autonomy- Mother’s Autonomy in Decision		X
Participant Satisfaction – Study specific form		X
Breastfeeding intent/uptake – Study specific form	X	X

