8.0 Data and Specimen Management

Data Analysis

Given the small scale of the pilot study, statistical analyses are intended to detect a signal rather than between-group differences. Preliminary analyses will focus on the distributional characteristics of the primary outcomes, in addition to conducting analyses for group baseline equivalency and participant attrition. Preliminary analyses will also examine group differences in demographics (e.g. age, education, gestation) at baseline. We will examine distributions using standard tests to detect outliers. For outcomes only measured at a single time point, analyses will consist of ANOVAs and Chi Square tests. For between-group contrasts ($df=1$) for measures expected to change over time (measured at baseline and PPFU) we will utilize the ANCOVA analog using multilevel modeling with outcome measures separately entered as a level 1 variable and group membership entered in level 2, with no protection for type 1 error. Meta analytic techniques⁴⁵ using mixed-model regressions will be used to determine overall impact of the intervention (all dependent variables entered into 1 distribution). The Q statistic will then be used to examine the homogeneity of the observed effect sizes associated with outcomes. Finding of heterogeneity will indicate that, on average, one or more outcomes are more sensitive to detecting treatment effects than others. Thus, we will identify those outcomes which provide the strongest signal. Given the nature of this rich dataset, many important analyses not directly tied to aims will be conducted (e.g. temporal patterns of relapse).

Power Analysis

Given the novelty of this pilot study, meaningful estimates of between group differences cannot be reasonably obtained or calculated. In fact, the objective of this study is to derive those estimates necessary for a future sufficiently powered R01 proposal.

Steps that will be taken to secure the data to maintain confidentiality

Most data will be collected electronically through a survey tool, such as Qualtrics. Some data are difficult to entirely collect this way (e.g. Timeline followback, SCID5) and will thus need to have values extracted from paper questionnaires or notes. Electronic data

PROTOCOL TITLE: Providing Expanded Continuous Labor Support to Pregnant Women in New Mexico with Substance Use Disorders

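### Section 8.0 pools the effects of all outcomes from the same 30 or so women and infants and tests them with Q, without stating how within-participant correlation is handled

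*Combined protocol and SAP*

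**What the plan says.** The Data Analysis text in Section 8.0 has two layers. First, outcomes are analysed one at a time. Those measured once get ANOVA or chi-square tests; for those measured at baseline and at the postpartum follow-up, "we will utilize the ANCOVA analog using multilevel modeling with outcome measures separately entered as a level 1 variable". Second, the outcomes are combined. A meta-analytic technique is cited, and "mixed-model regressions will be used to determine overall impact of the intervention (all dependent variables entered into 1 distribution". Then "The Q statistic will then be used to examine the homogeneity of the observed effect sizes associated with outcomes". The use made of the result is explicit: "Finding of heterogeneity will indicate that, on average, one or more outcomes are more sensitive to detecting treatment effects than others", and "Thus, we will identify those outcomes which provide the strongest signal".

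Sections 3.0 and 17.0 plan 34 women enrolled and 30 completing, 15 per group. Section 5.0 lists six primary outcomes (relapse, PTSD score, depression score, breastfeeding, neonatal abstinence syndrome, length of NICU stay) and four secondary ones. One of the four is "Doula Satisfaction". Section 6.0 says of it that "doulas will fill out a doula satisfaction survey online following each 2-week postpartum doula visit", and of allocation that "Women in G1 will be assigned a doula"; the comparison group has none. The chart-review section refers back to the same analysis text and adds nothing on this point.

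**The concern.** Standard meta-analytic pooling, and the chi-square reference for Q, assume that the effect sizes are independent, as they would be if each came from a separate study. Here each woman and infant contributes to every effect. The only multilevel model described is fitted to each outcome separately, so it links a woman's two time points but not her different outcomes. Nowhere do the documents mention a participant effect across outcomes, a between-outcome covariance, a robust variance or an assumed correlation.

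Positive correlation is plausible once outcomes are scored in the same direction. Section 1.1 describes substance use and trauma-related disorders as occurring together, and two of the primary outcomes are measured on the same infant. If that correlation is ignored, the interval for the overall impact is too short and a signal is declared too often. Q meanwhile loses what power it has to show that outcomes differ in sensitivity, which is its stated purpose.

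The set to be pooled is also not defined. Taken literally, all dependent variables would include doula satisfaction, which has no value in the comparison group and so gives no between-group effect.

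**Working it through.** The plan gives no alpha, power or effect size for this step, so there is no figure of its own to reproduce.

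**Inputs from the documents.** 15 completers per group (Section 17.0). k = 6 primary outcomes, or 9 with social support, autonomy and participant satisfaction (Section 5.0).

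**Assumed, because not stated.** Two-sided 5%; equal precision; a common correlation ρ of 0 to 0.5 between outcomes; signs aligned for benefit; one effect size per outcome, pooled conventionally.

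**Formulas.**
- Variance of one standardised effect: 2/15 = 0.133, so SE 0.365.
- Pooled SE if independent, k = 6: 0.365/√6 = 0.149; 95% half-width 1.96 × 0.149 = 0.29.
- With correlation, the pooled variance is multiplied by 1 + (k − 1)ρ.
- True error of the nominal 5% pooled test: 2[1 − Φ(1.96/√(1 + (k − 1)ρ))].
- Under homogeneity Q is distributed as (1 − ρ) times chi-square on k − 1 df, so its true size for k = 6 is P(χ²₅ > 11.07/(1 − ρ)).

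**Example, k = 6, ρ = 0.3.** The multiplier is 1 + 5 × 0.3 = 2.5. The error is 2[1 − Φ(1.96/1.58)] = 21%. The half-width needed is 0.29 × 1.58 = 0.46. The size of Q is P(χ²₅ > 15.8) = 0.7%. The six effects carry the information of 6/2.5 = 2.4 independent ones.

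**Results, k = 6.** Simulated values are from 20,000 trials per setting with Hedges g and inverse-variance weights.

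| ρ | 0 | 0.1 | 0.3 | 0.5 |
|---|---|---|---|---|
| Pooled-test error, formula | 5% | 11% | 21% | 30% |
| Pooled-test error, simulated | 4% | 10% | 20% | 28% |
| Half-width reported | 0.29 | 0.29 | 0.29 | 0.29 |
| Half-width needed, simulated | 0.29 | 0.35 | 0.45 | 0.54 |
| Size of Q, formula | 5% | 3.1% | 0.7% | 0.05% |
| Size of Q, simulated | 4.4% | 2.8% | 0.9% | 0.1% |
| Power of Q, one outcome at d = 0.8, five at 0 | 24% | 20% | 14% | 7% |

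The simulated half-widths at ρ above 0 are a little below the formula's because g carries the small-sample factor 1 − 3/(4 × 28 − 1) = 0.973.

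**Variations.**
- k = 9: simulated pooled error 4 / 13 / 28 / 37%.
- Random-effects pooling across outcomes, k = 6: 3 / 9 / 19 / 28%. A random effect for outcome alone does not repair the error.
- Uneven correlations (three maternal scores 0.5, the two infant outcomes 0.6, the rest 0.1): pooled error 16%, size of Q 2.4%, half-width 0.29 against 0.42 needed.
- Breastfeeding left in its natural direction while the other five are harm-coded: 5 of the 15 pairwise correlations turn negative, so the mean correlation is (10 − 5)/15 × ρ = ρ/3. Simulated pooled error falls to about 6 / 10 / 14% at ρ 0.1 / 0.3 / 0.5.
- Participant random intercept in a stacked model: overall test 5–6%; group-by-outcome test 4–7% with equal and 6–9% with uneven correlations.

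**The case against.** The strongest reply is that the plan speaks of mixed-model regressions, and such a model can hold a participant effect. The method source it cites is not visible here. A reader might infer that the plan assumes independence; the documents do not go that far. They leave the term unstated. That part of the objection stands, and it makes the numbers conditional. The wording still leans towards conventional pooling, because Q is applied to observed effect sizes, one per outcome.

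Second, this is a signal-seeking pilot whose overall hypothesis is feasibility, and it openly declines type 1 error protection for its between-group contrasts. That is fair as regards multiplicity. It does not cover an interval computed from the wrong standard error.

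Third, a reader might infer that the choice of outcomes for the later grant application is corrupted. It is not. In the scenario with one outcome at d = 0.8, that outcome's mean g is 0.79–0.80 at every ρ, and it has the largest g in 79 / 82 / 88 / 94% of trials at ρ 0 / 0.1 / 0.3 / 0.5. Ranking by effect size does not suffer; only the Q test in front of it does. Nor can exaggeration of the largest effect after Q rejects be blamed on correlation: it averages 1.20–1.25 whatever ρ is, so it is a separate matter.

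Fourth, ρ and the coding are assumed. That stands; hence the range, the zero case and the unaligned case.

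**Conclusion.** The concern holds as a gap in specification with a real consequence under the likelier reading. If effects are pooled conventionally, and outcomes scored for benefit are positively correlated, the overall-impact interval is too short and Q is too conservative. With six outcomes and 15 per group, a correlation as small as 0.1 takes the pooled error to about 10%, and 0.3 to about 20%. With breastfeeding coded the opposite way the figure at 0.3 is about 10%. At zero correlation the problem vanishes, and a fitted participant-level term largely removes it.

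The harm is confined to the overall-impact interval and the Q test. Effect sizes for single outcomes (Aim 2(d)), their ranking and the feasibility conclusion are untouched. Separately, and without any assumption, doula satisfaction cannot contribute a between-group effect, so the pooled set has to be listed. This should be corrected in Section 8.0 but does not threaten the study's main purpose. Confidence is medium, because the cited source and the correlations are unknown.

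**What to change.** In Section 8.0:

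1. List the pooled outcomes, limited to those with values in both groups (not doula satisfaction), and score each so that higher means benefit. Confirm that participant satisfaction is asked in comparable form in both groups, since Aim 1(c) connects satisfaction with doula services.
2. Estimate the overall impact from a per-woman average of the standardised outcomes, compared between groups with the available baseline scores as covariates; this keeps the planned baseline adjustment. State how a missing component is handled. Alternatively, fit a stacked mixed model with a participant random effect, which also uses women with some outcomes missing.
3. Replace the chi-square reference for Q by permutation of whole participants' within-group residuals, or use the group-by-outcome test from the stacked model with a Greenhouse–Geisser correction. Do not fit an unstructured covariance: six outcomes already need 6 × 7/2 = 21 parameters from about 30 women.
4. Report every outcome's effect size with its confidence interval.

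In simulation the baseline-adjusted composite had 4.4–6.4% error. The permutation Q had 4.3–6.4%, and about 7% when all six outcomes shared d = 0.5. The Greenhouse–Geisser test had 5.0–5.9%, but was checked only for normal, unadjusted outcomes.

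The cost is a few sentences, a short script and a wider pooled interval: half-width 0.37 / 0.48 / 0.57 for the composite at ρ 0.1 / 0.3 / 0.5, with power 77 / 55 / 43% if all six effects are d = 0.5. No new data are needed.

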1.2 Hypotheses

This is a feasibility study; therefore, the aims are to determine the feasibility of this research design in this context. Our overall hypothesis is that this study will be feasible in this population. We plan to also use this pilot data to calculate effect sizes to conduct power analyses for future research on this topic.

Aim 1. Feasibility – (a) Develop and refine participant recruitment and retention methods, (b) Develop and refine doula trauma and SUD training with input from a group

PROTOCOL TITLE: Providing Expanded Continuous Labor Support to Pregnant Women in New Mexico with Substance Use Disorders

of prior XXX Program patients (who gave birth with an SUD), (c) Estimate patient interest, satisfaction, and knowledge about doula services, (d) Estimate doula retention, satisfaction, and increased knowledge about SUD and trauma, and (e) Estimate patient attrition and follow-up rates.

Aim 2. Estimate behavioral health outcomes – (a) Traumatic birth outcome, (b) breastfeeding uptake, (c) SUD relapse and postpartum mental health change from baseline, (d) Estimate effect sizes of all theorized relationships.

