3.0 Study-Wide Number of Subjects

We plan to enroll 34 women in order to have a final number of 30 who complete the study.

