17.0 Number of Subjects

We will recruit up to 34 participants in order to have 30 who complete the study. We plan to recruit 17 participants for each group in order to have 15 who complete the study in each group.

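### Section 8.0 picks the strongest-signal outcomes and takes their effect sizes from the same 30 women; if an R01 is sized on those raw estimates, they are biased upward

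*Combined protocol and SAP*

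**What the plan says.** Section 8.0 (Data Analysis) plans ANOVA and chi-square tests for outcomes measured once, and a multilevel ANCOVA analog for outcomes measured at baseline and postpartum. The latter contrasts are run "with no protection for type 1 error"; for the single-time outcomes the plan is silent on multiplicity. All dependent variables are then pooled by meta-analytic methods and the Q statistic is used to test homogeneity of the effect sizes. Heterogeneity is read as showing that some outcomes are more sensitive than others, and the plan continues: "Thus, we will identify those outcomes which provide the strongest signal".

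On how the results will be used, section 1.2 says: "We plan to also use this pilot data to calculate effect sizes to conduct power analyses for future research on this topic". The Power Analysis paragraph of section 8.0 says that "meaningful estimates of between group differences cannot be reasonably obtained or calculated" for this pilot, and gives the derivation of estimates for an adequately powered R01 as the study's objective. Aim 2(d) in section 1.2 covers the effect sizes of all theorized relationships, not only the strongest.

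On size, section 17.0 says: "We plan to recruit 17 participants for each group in order to have 15 who complete the study in each group".

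No Q threshold, alpha, confidence interval, shrinkage, minimum important difference or rule for choosing the R01 outcome is stated.

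**The concern.** The same data would choose an outcome and supply its effect size. With 15 women per group, each standardised difference carries a standard error of about 0.37. The largest of ten such estimates is therefore partly the outcome with the largest true effect and partly the one with the most favourable sampling error. Its raw value overstates its true effect on average.

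Section 5.0 lists six primary outcomes without ranking them, so the strongest-signal step is the only rule in the document for preferring one outcome to another. If its output becomes the effect size in the R01 power calculation, the R01 will be too small for the effect it is likely to meet.

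**Working it through.** **Figures in the plan.** The only sample-size figures are 34 enrolled for 30 completers and 17 for 15 per group. They agree: 2 × 17 = 34, 2 × 15 = 30, implied loss 4/34 = 11.8%. There is no power calculation to reproduce.

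**Number of contrasts (section 5.0).** There are six primary outcomes. Relapse has two measures ("Relapse will be defined as percent drinking or drug use days postpartum and by drug screen at hospital admission results"), which makes seven. Of four secondary outcomes, doula satisfaction has no control group, which leaves three. Total 7 + 3 = 10, or 11 with the traumatic birth outcome of Aim 2(a).

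**Assumptions not in the documents.** Two-sided alpha 0.05; 80% power for the R01; true standardised differences; equal correlation between outcomes; all outcomes continuous, unadjusted and coded so that positive means benefit; Q tested at 0.05.

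**Precision.** SE of d ≈ √(2/15) = 0.365. The 95% half-width is 1.96 × 0.365 = 0.72, or 2.048 × 0.365 = 0.75 with t on 28 degrees of freedom.

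**Selection without the Q condition.** In 40,000 simulated pilots per setting, the largest Hedges g was taken and used to size an R01. Power was then evaluated at the selected outcome's true effect. Ten outcomes with equal true effects, at correlation 0 / 0.3 / 0.5:

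| True d | Mean largest observed d | Median R01 n per arm | n per arm needed | Median real power |
|---|---|---|---|---|
| 0.2 | 0.78 / 0.69 / 0.61 | 28 / 36 / 44 | 393 | 11 / 13 / 15% |
| 0.3 | 0.88 / 0.79 / 0.71 | 22 / 27 / 33 | 175 | 17 / 20 / 23% |
| 0.5 | 1.10 / 1.00 / 0.93 | 14 / 17 / 19 | 63 | 26 / 31 / 34% |

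Hand check at true d = 0.3, correlation 0.3, with n per arm = 2 × (1.96 + 0.8416)² / d² = 15.70 / d²:

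- At d = 0.79, 15.70 / 0.624 = 25.2, so 26. The simulated median is 27.
- At d = 0.30, 15.70 / 0.09 = 174.4, so 175.
- With 27 per arm and true d = 0.3, 0.3 × √(27/2) = 1.10. Power ≈ Φ(1.10 − 1.96) = Φ(−0.86) ≈ 20%.

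With only the six primary outcomes and true d = 0.3, the largest observed d averages 0.78 / 0.70 / 0.64 and median power is 20 / 23 / 27%.

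**Unequal true effects (10 outcomes, mean 0.3, correlation 0.3).**

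- SD 0.15: observed 0.84, true effect of the selected outcome 0.40, power 27%.
- SD 0.3: observed about 0.98, true about 0.61, power about 42%. The formula gives 15.70 / 0.98² = 16.3, so 17 per arm, against 15.70 / 0.61² = 42.2, so 43.

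**Adding the Q condition.** With 10 outcomes and equal true effects, the test opens in about 4% of runs at correlation 0, 0.5% at 0.3 and under 0.1% at 0.5. Across the equal-effect settings the figure is at most about 5%. With SD 0.15 it opens in 9%, 2% and 0.4%. When it opens with every true d equal to 0.3, the observed maximum averages about 1.2 to 1.3.

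**One outcome fixed beforehand.** Its estimate is unbiased on average and median R01 power is 81–82%. About half of such R01s still fall below 80% power, and 27–40% fall below 50%, for true d from 0.2 to 0.5. Prespecification removes the bias but not the imprecision.

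**The case against.** A reader might infer that the R01 will be sized on the winning outcome. No sentence says so: Aim 2(d) estimates every effect, and section 8.0 does not confine the estimates it wants for the R01 to the strongest ones. That stands, so every R01 power figure here is conditional on the raw selected estimate being used. What remains is that the plan names one selection rule and does not say how R01 inputs are derived after it.

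A reader might also infer that an intervention with no effect would still hand the R01 a strong outcome. Selection follows a finding of heterogeneity, and with no true differences that finding would be rare at a 0.05 threshold. The stronger claim therefore fails if the step is applied as written. But the plan gives no threshold and does not say what happens without heterogeneity. The usual Q also assumes independent effects, whereas these outcomes come from the same women.

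The simulation does not match the planned models. Baseline adjustment would tend to improve precision; binary outcomes such as breastfeeding uptake would generally be less precise. The outcomes are also diverse, so equal true effects may be unrealistic. With wide variation the selected outcome does tend to be a better one (true 0.61 against a mean of 0.3), and inflation is smaller but still present.

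Finally, this is a feasibility study that openly disclaims type 1 error protection for its repeated-measure contrasts. Aim 1 is untouched, so it would go too far to say that the study's purpose is defeated.

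**Conclusion.** The point holds in conditional form. If the R01 is sized on the raw effect size of an outcome selected for the strongest signal, that effect size is biased upward. This was so in every scenario tried. With 10 outcomes of equal true effect, median real power is 11–34% over true d 0.2 to 0.5 and correlations 0 to 0.5. In the wider-variation case (SD 0.3, correlation 0.3) it is about 42%. The Q step is not a safeguard, because the runs that pass it are the more inflated ones.

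These sizes rest on assumed alpha, R01 power, correlations and true effects, on continuous unadjusted outcomes, and, except where stated, on selection without the Q condition. The documents support neither the reading that the R01 will certainly be underpowered nor the reading that the pilot as a whole fails. This should be fixed, because deriving R01 estimates is a stated objective and the remedy is cheap.

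**What to change.** In section 8.0, after the strongest-signal sentence:

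1. State that neither the choice of R01 primary outcome(s) nor the R01 sample size will rest on the raw effect size of outcomes selected for the strongest signal.
2. Report every between-group effect size with a 95% confidence interval, whatever its magnitude.
3. Label any ranking of outcomes exploratory, and show a selection-corrected (shrunken or bootstrap) estimate beside the raw one.
4. Name the candidate R01 outcome(s) before any group comparison is seen, and size the R01 on a minimum important difference or a conservative confidence limit. With a half-width of about 0.7 SD, a lower 95% limit exceeds zero only if the observed d is above about 0.7, so a minimum important difference will usually be the workable choice.
5. Give the Q threshold, how correlation between outcomes is handled, and what follows if heterogeneity is not found.

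The cost is a few sentences, slightly more analysis work, and headline effect sizes that look less favourable. Recruitment, assessments and the feasibility aims do not change.

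### With 15 completers per group, the pilot's observed between-group effect is too imprecise, on its own, to size the R01 it is meant to inform

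*Combined protocol and SAP*

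**What the plan says.** Section 8.0 (Power Analysis) gives no power calculation, because "meaningful estimates of between group differences cannot be reasonably obtained or calculated". In context this means before the study is run. It continues: "In fact, the objective of this study is to derive those estimates necessary for a future sufficiently powered R01 proposal". The estimates referred to are the between-group differences of the preceding sentence.

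Section 1.2 makes feasibility the main purpose and then adds: "We plan to also use this pilot data to calculate effect sizes to conduct power analyses for future research on this topic". Aim 2(d) lists effect sizes for all the theorised relationships.

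Section 17.0 sets the information available: "We plan to recruit 17 participants for each group in order to have 15 who complete the study in each group". Section 3.0 gives the same totals, 34 enrolled for 30 completers.

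The plan gives no confidence level, precision target, smallest worthwhile difference, or rule for turning an observed effect into a sample size. On error control, section 8.0 says only that the between-group contrasts on repeated measures are made "with no protection for type 1 error".

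**The concern.** Section 8.0 offers the supply of effect estimates for the next trial in place of a power analysis. A required sample size varies with the inverse square of the effect, so moderate error in the effect becomes very large error in the size. With 15 per group the error in the effect is not moderate.

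An R01 planned on such an estimate could be too small to answer its question. It could also be dropped because the pilot effect happened to fall near or below zero, or be made needlessly large. The next trial would recruit from the same vulnerable population, so the cost of a wrong size is real even though it falls outside this study.

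**Working it through.** **The plan's own figure.** The implied loss is 4/34 = 11.8%, and 30/(1 - 4/34) = 34 (17 for 15 per group). This is circular, since no dropout rate is stated. The 15 per group cannot be re-derived, because no effect, alpha, power or precision is given.

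**Inputs.** From the documents: n = 15 completers per group. Assumed: continuous outcome, unadjusted two-group comparison, 95% interval, two-sided 0.05, 80% power, and observed d from 0.2 to 1.0.

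**Step 1: interval for an observed d of 0.5.** SE is about √(2/15) = 0.365, so 0.5 ± 1.96 × 0.365 gives -0.22 to 1.22. The exact noncentral-t interval is -0.23 to 1.22.

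**Step 2: R01 size implied by each value.** n per group = 2 × (1.96 + 0.84)² / d².

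- Point estimate 0.5: 2 × 7.85/0.25 = 62.8, so 63 (64 by t-test).
- Upper limit 1.22: 2 × 7.85/1.49 = 10.5, so 11 (12 by t-test).
- Lower limit -0.23: no finite size.

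**Step 3: other observed effects** (noncentral-t intervals; t-test size at the upper limit, normal formula at the lower).

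| Observed d | 95% CI | n at upper limit | n at lower limit |
|---|---|---|---|
| 0.2 | -0.52 to 0.92 | 20 | none |
| 0.3 | -0.42 to 1.02 | 17 | none |
| 0.4 | -0.33 to 1.12 | 14 | none |
| 0.5 | -0.23 to 1.22 | 12 | none |
| 0.7 | -0.04 to 1.43 | 9 | none |
| 0.8 | 0.05 to 1.54 | 8 | about 6,800 |
| 1.0 | 0.23 to 1.75 | 7 | about 300 |

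The upper end of the size range becomes finite once observed d passes about 0.75.

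**Step 4: consequence if the R01 were sized on the point estimate.** This rule is an assumption. True power is below 50% when n < 2 × (1.96/true d)². At true d = 0.4 that is n < 48, which happens when the observed d exceeds 0.4 × 2.80/1.96 = 0.57. The normal approximation gives P = 1 - Φ((0.57 - 0.40)/0.365), about 32%. Simulation with bias-corrected d gives 31%, and gives 35% and 27% for true d of 0.3 and 0.5. Pilots with a non-positive effect are not counted in these percentages.

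At true d = 0.4 (100 per group needed by t-test), P(observed d ≤ 0) = Φ(-0.40/0.365), about 14%. The interquartile range of the implied size is about 38 to 690 per group if those 14% count as infinite, and about 34 to 240 among pilots with a positive effect.

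**Step 5: sensitivity at observed d = 0.5.**

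- All 17 per group analysed: 13 to none.
- Baseline adjustment with correlation 0.5: CI -0.12 to 1.12, so 10 to none.
- 80% interval in place of 95%: 17 to about 25,600.
- A binary outcome, with invented counts: 8/15 against 5/15 implies 96 per group, 8/15 against 4/15 implies 52, and 7/15 against 5/15 implies 211. One event moves the size about twofold.

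**Step 6: what the pilot estimates better.** The pooled SD on 28 df is known to within factors of 0.79 to 1.35. Its one-sided 80% upper limit is √(28/χ² 20th percentile) = 1.14 times the estimate. Retention of 30/34 would have a 95% interval of 73% to 97%.

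**The case against.** The strongest reply is that this is a feasibility study and says so. Section 1.2 puts feasibility first and presents effect sizes as an additional use. Section 8.0 itself says that, at this scale, the analyses look for a signal and not for group differences. A reader might infer from the objective in section 8.0 that the study cannot meet its purpose. The documents do not support that: recruitment, retention, satisfaction and attrition under Aim 1 do not depend on the precision of an effect estimate.

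A reader might also infer that the R01 will be sized mechanically on the point estimate. The documents do not say this. Effect sizes can enter a power analysis through a conservative bound, a range, or in combination with other evidence. The risks in Step 4 are therefore conditional on a rule that the plan neither adopts nor excludes.

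Nor is it right that the plan ignores the more useful quantities. Aim 1 covers recruitment, retention, attrition and follow-up, and section 8.0 begins with outcome distributions and attrition. What is missing is a statement that these are what the next trial will be built on.

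Finally, the unadjusted standardised difference is not the planned analysis for repeated measures and does not fit the binary outcomes. That is fair, but Step 5 shows that neither adjustment nor a binary endpoint changes the conclusion.

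These points limit the claim. They leave standing that two sections assign the observed effects a planning role that 15 per group cannot support.

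**Conclusion.** The point holds in limited form and should be fixed. It does not bear on whether the pilot should run.

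Sections 1.2 and 8.0 say that the between-group effects will supply what a sufficiently powered R01 needs, but at this sample size the observed effect alone cannot do so. A range such as 12 per group to no finite size is not a property of the plan. It belongs to an observed d of 0.5 under the stated assumptions. Over observed d of 0.2 to 1.0 the lower end runs from 20 down to 7 per group, and the upper end is finite only above about 0.75. The 27% to 35% chance of an R01 with under 50% power rests in addition on point-estimate sizing.

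All these figures take one outcome chosen in advance. Section 5.0 lists six primary outcomes, and section 8.0 plans to identify those with the strongest signal. Carrying the strongest forward would add upward selection bias that is not counted here.

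**What to change.** Amend sections 1.2 and 8.0 to state that:

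- observed between-group effects will be reported with 95% confidence intervals and will not be the planning effect for the R01;
- the pilot supplies outcome SDs (with an upper confidence limit, for example the one-sided 80% limit, a factor of 1.14 at 28 df), comparison-group event rates, baseline-to-follow-up correlation, recruitment and retention;
- the R01 will be sized on a smallest worthwhile difference, fixed before outcomes by group are examined. The plan describes no blinding, so the timing has to be tied to that examination.

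The choice of the 80% limit is a convention and may be varied. The cost is a few sentences, with no added participants, visits or data. The downside is a less favourable-looking claim for the pilot.
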